#### 6.4 Secondary analysis: Side effects (safety)

We will assess the proportion of drop-outs at six months and test for differences in the proportion of drop-outs in the intervention arms compared with the 20 mg arm. We will use Fisher's exact test with an  $p$ -value of less than 0.05 (corrected for multiple testing, see Section 6.7) as a threshold to declare statistical significance.

#### 6.5 Tertiary analyses

We will perform two types of tertiary analyses: (i) sensitivity analysis on the primary and secondary endpoints using different methods than used in the primary and secondary analyses in order to assess sensitivity to choice of analyses pathway, assumptions, and missing data; and (ii) on tertiary endpoints.

##### 6.5.1 Sensitivity analyses of the primary endpoint

1. We will perform sensitivity analyses to the primary analyses where the threshold for being defined as a responder is varied  $\pm 10$  percentage points, to assess whether the overall conclusion of the trial is sensitive to the within study definition of what a *responder* is. Similarly, we will perform a tipping point analysis, where the threshold for being defined as a responder is changed until the result of the trial changes (either from a nonsignificant result to a significant result or vice versa).

2. Using absolute change in density instead of relative change to define a responder.
3. We will analyze data from all arms in a regression model (as opposed to one arm against another arm). I.e., responder status (a binary variable) will be used as the response variable in a logistic regression model, where dose allocation is the independent variable.
4. We will impute missing data (as described in Section 6.9) and re-perform the primary analysis using imputed datasets (in a multiple imputation protocol).
5. We will analyse the results using the recorded continuous endpoint (density reduction) instead of discretising the reduction into either *responder* or *non-responder*. We will use both relative and absolute density reduction as endpoints in this analysis.

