10.6.1 Demographics and baseline data

All data will be presented using descriptive statistics. Results will be presented in total, by treatment group, age and as menopausal status. Continuous variables will be summarised using number of women, mean, standard deviation, median, minimum and maximum. Categorical variables will be summarised using the number and percentage of women.

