groups of women treated with placebo, 1, 2.5, 5, and 10 mg compared to the group of women treated with 20 mg tamoxifen. We will use Fisher's exact test with an  $p$ -value of less than 0.05 (corrected for multiple testing, see Section 6.7) as a threshold to declare statistical significance. The non-inferiority margin is defined to be 16.7 percentage points; that is, we define non-inferiority to mean that the fraction of responders is not less than one third of the treated individuals (50% minus 16.7% = 33.3%). The null hypothesis is thus that the proportion of responders in women treated with placebo, 1, 2.5, 5, and 10 mg is 16.7 percentage points less than those women treated with 20 mg tamoxifen (i.e. the fraction of responders is less than one third). For rejection of the null hypothesis, the lower end of the confidence interval needs to be higher than -16.7%. For this to hold, the point estimate of an intervention arm can not be more than 5 percentage points lower than the percent responders in the 20 mg arm.

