## 6.6 Sample size

Since we have five intervention arms and since we do the primary analysis on a "per arm basis", we have five chances to show noninferiority of the primary endpoint and we therefore need to correct for multiple testing. Standard methods for correcting for multiple testing (according to the methods by Bonferroni or Holm) are too conservative in this context, since they

rely on an assumption of independence between the tests whereas the tests here are clearly correlated. We will instead use the resampling based step-down method suggested by Romano, Shaikh, and Wolf [6], which seamlessly handles correlated tests (see also Section 6.7). The correlation structure of the tests is unknown and we therefore assume that the multiplicativity leads to that the  $\alpha$  decreases from 0.05 to 0.03 in order to declare a significant results (correction by Bonferroni would lead to an  $\alpha$  of 0.01).

With 168 participants in each study arm, the lower limit of the observed one-sided 98.5% confidence limit for the difference will be expected to exceed the non-inferiority margin 16.7 percentage points with a 80% power, assuming that the expected difference in responders between two arms is 0 and the proportion responders in the 20 mg tamoxifen group is 50%. With an estimated 30% drop-out rate, 240 patients in each group need to be randomized.

The trial is powered for the primary analysis. However, we here also briefly investigate the power for showing *both* noninferiority with respect to the primary endpoint and superiority with respect to the secondary endpoint. With 240 participants randomized to each study arm, we have 79% power to show both noninferiority with respect to the primary endpoint and superiority with respect to the secondary endpoint assuming that the proportion of drop outs is reduced by two thirds (from 30% to 10%) and 67% power if the proportion of drop outs is reduced by 50% (from 30% to 15%). (For these calculations, we use the same assumptions about the correlation of the tests as for the analysis of primary endpoint.)

The computations are based on the following formula:

$$n = f(\alpha, \beta) \frac{\pi_s(100 - \pi_s) + \pi_e(100 - \pi_e)}{(\pi_s - \pi_e - d)^2},$$

where  $\pi_s$  and  $\pi_e$  are the true percent 'success' in the standard (20mg) and experimental treatment group respectively, and

$$f(\alpha, \beta) = [\Phi^{-1}(\alpha) + \Phi^{-1}(\beta)]^2,$$

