## 6.7 Adjustment for multiplicity, confounders, and heterogeneity

Since we have five treatment arms and therefore five comparisons, we will need to adjust for multiple testing. The treatment arms are correlated,

since they are defined by different doses of the same drug. Thus, standard adjustment for multiple testing using the methods by Bonferroni or Holm are too conservative. Instead, we will use the bootstrap based method suggested by Romano, Shaikh, and Wolf [6], which seamlessly handles correlated tests. The correlation structure of the tests is unknown and we therefore assume that the multiplicativity leads to that the  $\alpha$  decreases from 0.05 to 0.03 in order to declare a significant results (correction by Bonferroni would lead to an  $\alpha$  of 0.01).

We will perform subgroup analyses, where the subgroups are CYP2D6 polymorphism status (excellent, intermediate, poor metaboliser [5]). CYP2D6 polymorphism status will be handled as a categorical fixed effect variable. Other subgroups will likely be studied in non-prespecified analyses.

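### The planned comparisons of the arms on density adjust for no baseline covariate, although several are collected: a missed efficiency of unknown size, not an error

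*SAP*

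**What the plan says.** - **Primary comparison (SAP 6.3).** Each arm is compared with 20 mg on the proportion of responders: "We will use Fisher's exact test with an" adjusted significance threshold. The lower confidence limit must also lie above the margin. "The non-inferiority margin is defined to be 16.7 percentage points". No covariate is mentioned.
- **All-arm sensitivity regression (SAP 6.5.1, item 3).** Responder status is analysed "in a logistic regression model, where dose allocation is the independent variable". Dose is the only term named.
- **Continuous sensitivity analysis (SAP 6.5.1, item 5).** Density reduction is analysed as recorded, on the relative and the absolute scale. No model and no baseline term are given.
- **SAP 6.7.** The heading is "Adjustment for multiplicity, confounders, and heterogeneity". The text covers multiplicity and subgroups by CYP2D6 status. CYP2D6 enters as a fixed effect for the subgroup analyses. No confounder is named for the arm comparison.
- **Data available.** Baseline density is needed to define the endpoint (SAP 6.3). Age and menopausal status are used in the descriptive tables: "Results will be presented in total, by treatment group, age and as menopausal status" (Protocol 10.6.1). Weight and height are measured at the baseline visit (Protocol 7.1.3).
- **Randomisation (Protocol 7.11.5).** Blocks are balanced over the six arms. No stratification factor is stated.
- **Where such variables are used.** Recorded densities, age and HRT status enter the multiple-imputation model of SAP 6.9, which serves a sensitivity analysis. The comparison then run on the imputed data is still the unadjusted one.

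**The concern.** The plan treats age, hormonal status and density as relevant to the density outcome. It imputes 6-month density from age, HRT status and recorded densities (SAP 6.9), and it excludes users of exogenous sex hormones because hormones affect density (Protocol 8.2). None of this reaches the models that compare the arms.

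If these variables predict response, a standardised comparison would give a narrower interval from the same women. That matters because the plan has little slack. SAP 6.3 notes that an arm can be at most about 5 points below 20 mg and still be declared non-inferior. All five comparisons share the 20 mg arm, so a chance imbalance in that arm moves all five together. If such an imbalance is seen after unblinding and no adjusted analysis was prespecified, SAP 1 would have any adjusted result labelled as unplanned.

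**Working it through.** **Inputs from the documents.** 168 evaluable women per arm, 50% responders in both arms, true difference 0, margin 16.7 points and a one-sided 98.5% limit (SAP 6.6 and 6.3). Normal quantiles: 2.170 for 98.5% and 0.842 for 80% power.

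**1. The plan's own size, unadjusted.**
n = (2.170 + 0.842)² × (50×50 + 50×50) / 16.7² = 9.07 × 5000 / 278.89 = 162.6, so 163 per arm. The stated 168 is slightly larger.
Power at 168: standard error = √(5000/168) = 5.455 points; Φ(16.7/5.455 − 2.170) = Φ(0.891) = 81.4%.
Half-width = 2.170 × 5.455 = 11.8 points, leaving 16.7 − 11.8 = 4.9 points. This matches the 5 points in SAP 6.3.
The stated power therefore holds without adjustment, on the plan's normal approximation.

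**2. What standardisation could add.** The variance of a covariate-standardised risk difference is about (1 − R²) times the unadjusted variance, where R² is the share of variance in responder status that the covariates explain. The documents give no R², so the responder rates below are assumptions. For one binary factor with rates p₁ and p₂, and prevalence q chosen so that overall response is 50%:
R² = q(1 − q)(p₁ − p₂)² / 0.25

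| Assumed rates | q | 1 − R² | Simulated variance ratio | Power at 168 | Half-width (points) | Largest shortfall allowed (points) |
|---|---|---|---|---|---|---|
| 50/50% | 0.50 | 1.00 | 1.00 | 81.4% | 11.8 | 4.9 |
| 60/40% | 0.50 | 0.96 | 0.96 | 83% | 11.6 | 5.1 |
| 65/37% | 0.46 | 0.92 | 0.93 | 84% | 11.4 | 5.3 |
| 75/30% | 0.44 | 0.80 | 0.81 | 89% | 10.7 | 6.0 |

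The simulation used 168 women per arm and set the threshold at the sample median of the 20 mg arm. Power = Φ(16.7/(5.455 × √ratio) − 2.170). Example: ratio 0.81 gives Φ(16.7/4.910 − 2.170) = Φ(1.231) = 89%.

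**3. Size of a chance imbalance.** For a factor with 50% prevalence (assumed), the between-arm difference in prevalence has SD √(2 × 0.25/168) = 5.5 points. A two-SD gap of 10.9 points moves the crude difference by 10.9 × (p₁ − p₂): 2.2 points at 60/40%, 3.1 at 65/37% and 4.9 at 75/30%. The unadjusted interval already allows for this variation.

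**4. Why adding covariates to the item 3 regression is not enough.** Simulation with one normal covariate and no true dose effect:

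| R² with responder status | SE of log odds ratio, adjusted (unadjusted 0.219) | Variance ratio, standardised risk difference |
|---|---|---|
| 0.06 | 0.226 | 0.92–0.95 |
| 0.16 | 0.240 | 0.83–0.86 |
| 0.31 | 0.269 | about 0.67 |

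The adjusted odds ratio has a wider interval and is a different estimand. The gain appears on the risk-difference scale, where the margin is defined.

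**5. Continuous change.** ANCOVA leaves about (1 − ρ²) of the variance of change, where ρ is the correlation of change with baseline density. The documents give no ρ. As an illustration, ρ = 0.3 leaves 1 − 0.09 = 0.91 and ρ = 0.5 leaves 1 − 0.25 = 0.75.

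**The case against.** The strongest reply is that nothing in the plan fails. A randomised comparison without covariates is unbiased on average, its interval already carries chance imbalance, and the stated power is met. This stands. A reader might infer that chance imbalance invalidates the result or that the trial is underpowered; the documents support neither.

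A reader might also infer that free precision is certainly being thrown away. The documents give no association between responder status and age, menopausal status, BMI or baseline density, so the gain could be close to zero. This stands too, and is why the sizes above are conditional.

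Baseline density is not ignored, because the endpoint is change from baseline. As a covariate it may add little on the responder scale. For item 5 of SAP 6.5.1, the fair description is that no model is specified, not that a model without baseline was chosen.

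It would be too strong to say that randomisation is unstratified. The protocol states no stratification factor, and that is all that can be said.

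Last, making a standardised estimate primary has a price. The threshold definition fixes the crude 20 mg rate at 50%, so that the margin reads as one third. A standardised 20 mg rate would no longer equal exactly 50%. This favours a supportive role. It does not argue against prespecifying the analysis.

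**Conclusion.** The point holds as a missed efficiency and an incomplete section of the SAP. No planned comparison of the arms on density names a baseline covariate for adjustment, and SAP 6.7 announces confounders without listing any. The unadjusted primary analysis is valid and reaches 81.4% power at 168 per arm.

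Under the assumed responder rates, standardisation would raise power to about 83%, 84% or 89%. With uninformative covariates the gain is zero. These figures rest on 50% response in both arms, no true difference, 168 analysed women per arm, a single binary factor and the plan's normal approximation. Neither the validity of the trial nor its sample size depends on this change.

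**What to change.** Before database lock, which Protocol 10.6 sets as the deadline for finalising the SAP:

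1. Prespecify, for each dose against 20 mg, a difference in responder proportion standardised from a logistic model with dose, baseline density, age, menopausal status and BMI. Judge it against the same 16.7-point margin.
2. Use a bootstrap interval that re-estimates the 20 mg median threshold in each resample.
3. Report it beside the unadjusted result, at least as a supportive analysis. Do not use the odds ratio from the adjusted model for this purpose.
4. Specify ANCOVA with baseline density for the continuous analyses in SAP 6.5.1, item 5.
5. List these covariates in SAP 6.7 and say that baseline-visit values are used. Protocol 7.1.3 lists weight and height after randomisation at that visit, under blinding.

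The cost is SAP wording and a little more programming, with no new data. The one trade-off is that the standardised 20 mg rate will not be exactly 50%, which the SAP should say.

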### **6.5.2 Sensitivity analyses of the primary and secondary endpoints simultaneously**

We will perform an analysis where the distance to the diagonal line in a plot of proportion responders vs proportion drop-outs by study arm is quantified (see Figure 2 for a schematic mock figure). Putatively, the arm with the greatest distance to the diagonal line gives the best tradeoff between efficacy and drop-out level. Confidence intervals of the distance will be computed using the bootstrap.

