Tertiary objectives: Relate levels of tamoxifen metabolites, proteins, lipids and hormones in blood and changes in breast tissue to different tamoxifen doses. Measure genetic polymorphism in germline DNA and relate it to the other tertiary objectives. Measure mammographic density and levels of side effects 6 months after tamoxifen cessation in relation to treatment arm

Tertiary endpoints: Levels of tamoxifen metabolites, proteins, lipids and hormones in blood. Breast tissue changes. Genetic polymorphism in germline DNA. Mammographic density and levels of side effects 6 months after tamoxifen cessation

Study design

Randomized, double blinded, six-armed, placebo controlled clinical trial

Number of subjects planned

1,440

Diagnosis and main eligibility criteria

Healthy women participating in mammographic screening with a a measurable mammographic density, i.e. ≥4.5 % density (volumetric) measured by Volpara.

Investigational Medical Product

Investigational product - Tamoxifen

Dosage – 20 mg, 10 mg, 5mg, 2.5 mg, 1 mg and 0 mg (placebo)

Oral administration, one tablet once daily

Duration of treatment

6 months

Duration of subjects involvement in the study

6 months for the SÖS-cohort (1400 particip), 12 months for the Lund cohort (40 paticip)

Efficacy assessments

Mammographic density after 6 months

Plasma levels of tamoxifen metabolites, proteins, lipids and hormones in blood

Genetic polymorphism measured in germline DNA

Safety assessments

Monitoring and recording of all AEs and SAEs

Statistical methods

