7.11.5 Method of assigning participants to treatment groups

Randomisation will be performed by a CMO (Galenica AB). The participants will be randomized in blocks in where the 6 arms are distributed evenly. The study participant emergency code envelopes are kept by a 24/7 service provider (Apoteket AB in Lund) during the whole study. Researchers do not have access to the randomisation list. This means that the study is triple blinded, i.e. neither study participant, Karma Study Centre, nor researchers know which medication product was used for each study participant.

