### **6.5.3 Tertiary endpoints**

Tertiary outcomes will be analysed with statistical methods appropriate for the specific outcome. A large number of tertiary endpoints are being recorded within the trial, e.g. levels of tamoxifen metabolites, proteins, lipids and hormones in blood, breast tissue changes, genetic polymorphism in germline DNA, mammographic density and levels of side effects 6 months after tamoxifen cessation. Since this is the first study of its type, the associations of nearly every possible combination of primary, secondary, and tertiary endpoints are of interest. We therefore expect a number of tertiary analyses to be performed. In the list below, we briefly specify some obvious examples of such analyses:

1. The association of dose of tamoxifen to blood concentration of tamoxifen metabolites (e.g. endoxifen) by CYP2D6 polymorphism status (a woman can be classified as an excellent, intermediate, or poor

[figure not shown]

Figure 2: Schematic picture of what a plot of proportion responders vs proportion drop-outs by study arm may look like. The arm with the greatest distance to the diagonal line gives the best tradeoff between efficacy and drop-out level.

metaboliser of tamoxifen based on polymorphism patterns in CYP2D6 [5]) will be analysed in a linear regression model with tamoxifen dose, CYP2D6 polymorphism status, and age as independent variables.

2. The association of plasma concentrations of endoxifen with responder status will be analysed with logistic regression both within treatment groups and among treatments groups (treatment group will be handled as a random effect in the latter case).

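### SAP 6.5.2 reads the best trade-off off the largest of six estimated distances but plans only intervals for the distance itself, which cannot show whether the leading arm differs from the others

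*SAP*

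**What the plan says.** SAP 6.5.2 quantifies how far each arm lies from the diagonal "in a plot of proportion responders vs proportion drop-outs by study arm". It then states: "Putatively, the arm with the greatest distance to the diagonal line gives the best tradeoff between efficacy and drop-out level". The caption of Figure 2 repeats the rule without the hedge: "The arm with the greatest distance to the diagonal line gives the best tradeoff between efficacy and drop-out level". Uncertainty gets one sentence: "Confidence intervals of the distance will be computed using the bootstrap".

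No confidence level is given. No contrast between arms, no measure of how certain the ranking is, and no allowance for having looked for the maximum is planned. The multiplicity method in SAP 6.7 is described for the five comparisons with 20 mg, not for a choice among six arms. SAP 6.3 defines a responder by the median decrease in the 20 mg arm. Section 6.5.2 does not say whether that median is re-estimated in each bootstrap resample.

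SAP 6.5 places this work among the tertiary analyses, as "sensitivity analysis on the primary and secondary endpoints using different methods than used in the primary and secondary analyses".

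**The concern.** Which arm has the best trade-off is a question about differences between arms. Six separate one-arm intervals do not answer it. The arm that comes out on top is partly there by chance, so its observed distance tends to exceed its true distance when competitors are close, and its ordinary interval misses mostly on the optimistic side.

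Close arms are plausible here. The introduction to the protocol reports that the pilot saw no difference between 10 and 20 mg in density reduction or side effects. SAP 6.6 assumes a zero difference in responders between arms. If response and drop-out both rise with dose, they offset each other on this scale.

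At stake is how firmly a reader could believe that one dose offers a better balance than its neighbours. Among the planned analyses, this is the one that combines response and drop-out in a single measure and names a leader.

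**Working it through.** **Inputs from the documents.** Six arms with equal allocation ("The participants will be randomized in blocks in where the 6 arms are distributed evenly"). SAP 6.6 gives 168 evaluable and 240 randomised women per arm, 50% responders at 20 mg, 30% drop-out, and alternatives of 10% and 15% drop-out. The documents give no dose-specific rates, so all other rates below are assumptions, as is the 95% level.

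**The plan's own figure.** With one-sided 1.5% error, 80% power, 50% responders in both arms and a margin of 0.167: n = (2.170 + 0.842)² × 0.50 / 0.167² ≈ 163. The SAP's 168 is within 3% of this (power at 168 is 81.4%), and 168 / 0.7 = 240. These sizes are used below.

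**Standard error of one distance.** With R the responder proportion and D the drop-out proportion, the signed distance is (R − D)/√2. At R = 50% and D = 30% the true distance is 0.20/√2 = 0.141. The standard error is √(0.25/168 + 0.21/240)/√2 = 0.0486/1.414 = 0.034.

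**Closed form, k equally good independent arms.** The leader's 95% interval covers with probability 0.975^k − 0.025^k. Its mean overstatement is the expected maximum of k standard normals times 0.034.

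| k tied best arms | Coverage | Overstatement |
|---|---|---|
| 1 | 95.0% | 0 |
| 2 | 95.0% | 0.019 |
| 3 | 92.7% | 0.029 |
| 4 | 90.4% | 0.035 |
| 5 | 88.1% | 0.040 |
| 6 | 85.9% | 0.044 |

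**Simulation.** The independent-arms column uses normal-theory intervals, with 15,000 to 200,000 trials per pattern. The last column lets all arms share a threshold estimated from the 20 mg arm. It comes mostly from a percentile bootstrap that re-estimates the threshold (1,500 trials, 400 resamples). The entries marked * come from separate simulations with a shared estimated threshold. Rates run from placebo to 20 mg.

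| Pattern | Overstatement | Independent arms | Shared threshold |
|---|---|---|---|
| All six at R 50%, D 30% | 0.043 | 84-85% | 89.8% |
| All six at R 50%, D 20% | 0.042 | 84.7% | about 88-90%* |
| Five equal, placebo worse | 0.040 | 86.6% | 91.2% |
| R 30/40/45/50/50/50%, D 10/15/20/25/30/30% | 0.034 | 87.0% | 92.3% |
| R 20/35/42/48/50/50%, D 10/12/15/18/25/30% | 0.028 | about 90% | about 92%* |
| Three equal best | 0.029 | 91.8% | not run |
| Two equal best | 0.016 | 94.6% | not run |
| R 25/33/50/50/50/50%, D 10/10/10/15/30/30% | 0.011 | 94.8% | 96.1% |
| One clear best (R 50%, D 10%; the others D 30%) | about 0 | 94.9% | 95.0% |

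In the fifth pattern the true distances are 0.071, 0.163, 0.191, 0.212, 0.177 and 0.141. The best arm leads the next by 0.021, less than one standard error, and it comes out on top in only 55% of trials. Exact ties are therefore not needed for the problem to appear.

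**Threshold held fixed.** If the bootstrap keeps the observed 20 mg median fixed, coverage falls to about 75-80% in the close-arm patterns. This is mainly a separate effect: even without any selection, coverage in the other five arms is then about 81-88%. The SAP leaves this choice open.

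**The case against.** The strongest reply is that this is a descriptive tertiary analysis and that the word putatively already limits the claim. Six distances with six intervals would let a reader see the overlap, and per-arm intervals are legitimate for that purpose. This stands as to weight. It does not supply the missing contrast, because overlap of separate intervals is a poor guide to a difference, particularly when the arms share an estimated threshold.

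Some stronger readings are tempting and are not supported:

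- A reader might infer that the intervals always cover only 85-91%. That needs several nearly tied arms, and the lower end needs all six tied (placebo included) and independent. The shared 20 mg median breaks that independence and raises coverage to about 88-92%. With one or two clear leaders it is about 95%, and the SAP's own scenario of drop-out falling from 30% to 10% can produce one.
- A reader might infer that this rule chooses the dose, or that only the leading arm would be reported. The documents say neither. The primary objective is the minimal non-inferior dose, tested against 20 mg with a multiplicity adjustment, and section 6.5.2 computes the distance for every arm.
- A reader might infer that an unsigned distance would rank a bad arm as good. The stated purpose implies a direction, and the figure is not available in the text reviewed. Writing the distance as signed is a clarification only.

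**Conclusion.** The concern holds in a limited form. As written, section 6.5.2 cannot show whether the leading arm differs from the rest. When several arms are close, the leader's distance is overstated by about 0.03 to 0.04. With the SAP's sample-size rates in every arm, that is about 0.043 on a true 0.141, or 30%. Nominal 95% coverage then drops to roughly 85-90% under independence, or 88-92% with the shared threshold re-estimated. When one or two arms stand out, coverage is near 95%; the overstatement is negligible with a single clear leader and about 0.016 to 0.019 with two tied leaders.

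These sizes rest on an assumed 95% level, assumed dose-specific rates, and a responder proportion taken over the 168 women expected to be evaluable. This is a worthwhile refinement of a sensitivity analysis and does not affect the trial's formal conclusions.

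**What to change.** Amend section 6.5.2 to specify the following:

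1. Resample women within arms, keeping each woman's response and drop-out status together. In each resample, re-estimate the 20 mg median threshold and recompute all six signed distances, (responders minus drop-outs)/√2.
2. State the confidence level.
3. Report the share of resamples in which each arm ranks first, as a descriptive measure of how stable the ranking is.
4. Report intervals for the difference in distance between the leading arm and each other arm. Do not describe one arm as the better trade-off than another unless that interval excludes zero.
5. Carry the hedge from the text into the Figure 2 caption.

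The cost is a few lines of code in a bootstrap that is already planned and a short SAP edit, with no new data. The downside is that the stated certainty about the best arm will be lower.
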